6.1 Expected Toxicities

6.1.1 Adverse Event List(s) for contrast mammogram

Risk of toxicity is related to the contrast agent that is administered during the imaging exam. Risks include allergic, allergic-like, or physiologic type of reaction to the contrast agent. There is also the risk for contrast induced nephropathy.

Risk of toxicity is also related to the risk of biologic harm from radiation administered during the exam. However, this risk is non-measurable during the course of this study.

6.2 Adverse Event Characteristics

- **CTCAE term (AE description) and grade:** The descriptions and grading scales found in the revised NCI Common Terminology Criteria for Adverse Events (CTCAE) version 4.0 will be utilized for AE reporting. All appropriate treatment areas should have access to a copy of the CTCAE version 4.0. A copy of the CTCAE version 4.0 can be downloaded from the CTEP web site http://ctep.cancer.gov/protocolDevelopment/electronic_applications/ctc.htm.

- **For expedited reporting purposes only:**
 - AEs for the agent(s) that are listed above should be reported only if the adverse event varies in nature, intensity or frequency from the expected toxicity information which is provided.
 - Other AEs for the protocol that do not require expedited reporting are outlined in the next section (Expedited Adverse Event Reporting) under the sub-heading of Protocol-Specific Expedited Adverse Event Reporting Exclusions.

- **Attribution of the AE:**
 - Definite – The AE *is clearly related* to the study treatment.
 - Probable – The AE *is likely related* to the study treatment.
 - Possible – The AE *may be related* to the study treatment.
 - Unlikely – The AE *is doubtfully related* to the study treatment.
 - Unrelated – The AE *is clearly NOT related* to the study treatment.

6.3 Expedited Adverse Event Reporting

6.3.1 Investigators **must** report to the Overall PI any serious adverse event (SAE) that occurs after the initial dose of study treatment, during treatment, or within 30 days of the last dose of treatment on the local institutional SAE form.

6.3.2 DF/HCC Expedited Reporting Guidelines

Investigative sites within DF/HCC will report AEs directly to the DFCI Office for Human Research Studies (OHRs) per the DFCI IRB reporting policy.

Attribution	DF/HCC Reportable AEs				
	Gr. 2 & 3 AE Expected	Gr. 2 & 3 AE Unexpected	Gr. 4 AE Expected	Gr. 4 AE Unexpected	Gr. 5 AE Expected or Unexpected
Unrelated Unlikely	Not required	Not required	5 calendar days [#]	5 calendar days	24 hours*
Possible Probable Definite	Not required	5 calendar days	5 calendar days [#]	5 calendar days	24 hours*
[#] If listed in protocol as expected and not requiring expedited reporting, event does not need to be reported.					
* For participants enrolled and actively participating in the study or for AEs occurring within 30 days of the last intervention, the AE should be reported within 1 business day of learning of the event.					

6.4 Expedited Reporting to Hospital Risk Management

Participating investigators will report to their local Risk Management office any participant safety reports or sentinel events that require reporting according to institutional policy.

6.5 Routine Adverse Event Reporting

All Adverse Events **must** be reported in routine study data submissions to the Overall PI on the toxicity case report forms. **AEs reported through expedited processes (e.g., reported to the IRB, FDA, etc.) must also be reported in routine study data submissions.**

7. IMAGING AGENT INFORMATION

A list of the adverse events and potential risks associated with the investigational or other agents administered in this study can be found in Section 7.1.

8. STUDY CALENDAR

	Visit 1 ^a
	Screening & exam
Informed Consent	X
Medical History	X
Urine pregnancy Test	X ^b
Blood Test	X ^b
Contrast Mammogram	X

^a If abnormal findings are detected on the contrast mammogram, there is the potential that additional standard of care tests and procedures will need to be performed. These may occur on the same day of the contrast mammogram or at a later date.

^b Blood and urine samples will be taken if standard of care samples are not available.

9. MEASUREMENT OF EFFECT

9.1.1 Methods for Evaluation of Disease on Conventional mammography, ultrasound

Two radiologists will retrospectively and independently review the pre-biopsy mammogram and ultrasound that had been performed for clinical purposes. They will each provide a BI-RADS code of the biopsied area based on the combined assessment of the relevant pre-biopsy imaging. If there is a discrepancy in interpretation, then a third radiologist will be the tie-breaker.

9.1.2 Methods for Evaluation of Disease on CESM

Two radiologists will prospectively review the CESM, and will use a third as tie-breaker. The CESM will be evaluated for the biopsy site and up to two additional findings in either breast. The biopsy site will be evaluated for abnormal findings that would suggest malignant involvement such as abnormal enhancement around the biopsy site, abnormal calcifications or masses. The result of the consensus will be documented in the clinical

report.

All measurements should be taken and recorded in metric notation using a digital measurement tool. A BI-RADS code will be assigned to each finding. This code provides a probability of malignancy score as well as a management recommendation.

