1.1 Study Design

This is a prospective clinical pilot study evaluating whether CESM can predict upgrade rates to malignancy at the time of surgical excision. All study participants with a diagnosis of ADH on core needle biopsy, who will be getting subsequent surgical excision, will have a CESM prior to surgical excision. CESM outcomes will be compared with the surgical outcomes to determine whether CESM can predict upgrade to malignancy.

Study Population: Women \geq 30 years of age with a diagnosis of ADH identified by ultrasound and stereotactic core biopsy who will be getting subsequent surgical excision will be included in this study.

Recruitment and Enrollment: No formal publicity of the research study will be performed. Subjects will be approached for study participation by a research coordinator after their diagnosis of ADH and completed diagnostic work-up for this diagnosis. Interested subjects will then be enrolled in the study.

Image acquisition: CESM will be performed according to BIDMC clinical protocols for image acquisition. Omnipaque 350 (the standard CT contrast agent) will be used at a dose of 1.5 mL of contrast per kilogram of body weight at an injection rate of 3 mL/second to a maximum in dose of 150 ml. The patient's weight will be confirmed with measurement on a scale by the technologists, as is done in clinical practice, and documented on both clinical forms and case report forms.

Image interpretation: Two radiologists will independently interpret the CESM exam. Radiologists will have access to all the pertinent prior history and routine imaging. Each radiologist will document their interpretation of the biopsy site and up to 2 additional findings per exam using the Breast Imaging-Reporting and Data System (BI-RADS). The radiologist will also provide a BI-RADS code for the overall exam. If there is a discrepancy in interpretation for any finding, then a third radiologist will be the tie-breaker. The description of the site of atypia will be excluded from the clinical report and will be entered into a research note to be included in the online medical record. This will ensure that the surgeon will not be biased by the CESM interpretation of the area of atypia. In addition, all individual and final interpretations will be documented in the case report forms. Incidental findings identified on CESM (defined by >2 cm away and distinct from the biopsied mass) will be managed according to standard of care.

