5. TREATMENT AND/OR IMAGING PLAN

The CESM exam will be performed according to clinical protocol. Omnipaque 350 (the standard CT contrast agent) will be administered at a dose of 1.5 mL of contrast per kilogram of body weight at an injection rate of 3 mL/second, according to clinical protocol. Images will be acquired within approximately 2-12 minutes of contrast injection. A low energy and high energy image will be acquired of each breast in two projections for a total of four images per breast. The voltage will be based on breast tissue thickness and will conform to the Mammography Quality Standards Act guidelines for quality control. The total radiation dose of CESM has been shown to be approximately 20-80% greater than the dose of a standard mammogram (11,12). Please see 1.1 above for the detailed study design.

A clinical report will be generated and entered into the online medical record. The description of the site of atypia will be excluded from the clinical report and will be entered into a research note to be included in the online medical record. This will ensure that the surgeon will not be biased by the CESM interpretation of the area of atypia.

All incidental areas identified on the CESM study (>2cm away and distinct from the biopsied mass) will be managed according to standard of care.

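### Section 9.1.2 sends the CESM consensus, biopsy site included, to the clinical report, while 1.1 and 5 keep the atypia-site read out of it, so the surgeon's masking is not assured as written

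*Combined protocol and SAP*

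**What the plan says.** Section 1.1 (Image interpretation) states the masking rule: "The description of the site of atypia will be excluded from the clinical report and will be entered into a research note". Section 5 repeats it. Both give the purpose, which is to prevent the CESM read of the atypia from influencing the surgeon.

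Section 9.1.2, which sets out how the CESM is read, says "The CESM will be evaluated for the biopsy site and up to two additional findings in either breast". It describes what is sought at the biopsy site and then says "The result of the consensus will be documented in the clinical", the sentence ending with the word report after a page break. It adds that every finding receives a BI-RADS code: "This code provides a probability of malignancy score as well as a management recommendation".

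Three other statements matter:

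- **Medical record.** Section 5 says "A clinical report will be generated and entered into the online medical record", and that the site description is "entered into a research note to be included in the online medical record".
- **Overall code.** Section 1.1 says "The radiologist will also provide a BI-RADS code for the overall exam". Section 11.1 sets the overall code by the most suspicious finding.
- **Case report forms.** Section 1.1 says "In addition, all individual and final interpretations will be documented in the case report forms".

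**The concern.** Staff who follow 9.1.2 literally would put the biopsy-site result in the document from which 1.1 and 5 exclude it. Nothing in 9.1.2 limits its sentence to the additional findings or refers back to the masking rule.

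The primary outcome in 11.1 compares the biopsy-site CESM code with the pathology of the excised specimen. Under 3.1.4 every participant is to have excision, so whether surgery takes place does not depend on CESM. How much tissue is removed, or from where, could depend on it if the surgeon knew the site read. The reference standard would then depend in part on the test being evaluated, which is what the masking is meant to prevent. This step is an inference from the design; the documents do not state it.

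The descriptive secondary outcome is also affected. Sections 1.1 and 9.2.1 record the initial plan, the final treatment and any procedures that CESM set in motion. They do not record what CESM information the surgeon had. If a plan changed, it could be unclear whether the site read or a finding elsewhere was the reason.

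**Working it through.** The point depends on no rate, power or sample-size figure, so the check is a comparison of texts.

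**1. What the consensus covers.** Under 9.1.2 the read covers the biopsy site and up to two other findings, by two radiologists with a third as tie-breaker. The consensus therefore includes the biopsy site.

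**2. Where the consensus goes.**

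| Section | Biopsy-site read | Other findings |
|---|---|---|
| 1.1 | Research note in the online medical record, not the clinical report; also the case report forms | Not excluded from the clinical report; also the case report forms |
| 5 | Research note in the online medical record, not the clinical report | Not excluded from the clinical report |
| 9.1.2 | Clinical report (no exception stated) | Clinical report |

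The three sections agree on the other findings. For the biopsy site, 9.1.2 read literally says the opposite of 1.1 and 5.

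**3. Whether the documents settle it.** No statement of precedence was found, and 9.1.2 contains no cross-reference to 1.1 or 5.

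**4. Whether masking is secure if 1.1 and 5 govern.** The clinical report and the research note are both placed in the online medical record. No section says who may open the note before excision. Leaving the site read out of one document protects the surgeon only if the other is not open to the surgeon, and the protocol does not say that it is closed.

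**5. The overall code.** By 11.1, overall code = the most suspicious of (site code, codes of the additional findings). Codes 1 to 3 count as negative, and 4 and 5 as positive. Suppose the overall code were shown in the clinical report:

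- An overall code of 1, 2 or 3 would mean that the site is negative, since the site code cannot exceed the overall code.
- An overall code of 4 or 5, with no other finding coded that high, would mean that the site is positive, and the overall code would equal the site code.

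In both cases the code would disclose the site result even with the description removed. The documents do not say whether the overall code appears there, so this is a gap to close and not a second contradiction.

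**6. Reach.** Section 11.2 plans 6 malignant + 24 benign = 30 participants, the total in its accrual table. The recording rule applies to all of them.

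**The case against.** The strongest reply is that the text can be reconciled as it stands. The exclusion is specific, appears twice and carries its reason, and section 5 sends the reader to 1.1 for the detailed design. The 9.1.2 sentence is general, does not mention the surgeon and looks like a drafting omission. Section 1.1 also separates the channels: the site description goes to the research note, all reads go to the case report forms, and incidental findings more than 2 cm away follow standard of care. On this view a short qualifier in 9.1.2 ends the matter, and a 30-patient pilot meant to inform a larger study needs no more.

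Much of this stands. The rule in 1.1 and 5 is probably the intended one, and that lowers the severity. It does not remove the point. Precedence is left to inference, in the section that staff would consult when reading the CESM, and the access gap for the research note remains on the favourable reading too.

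A reader might go further, in three ways that the documents do not support:

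- **That the surgeon will see the site read.** The absence of a stated access limit does not show that the surgeon has access or uses it.
- **That CESM decides who receives the reference standard.** All participants are to have excision, so there is no selective verification of this kind. Only extent or target is in question.
- **That the overall code discloses the site result.** It would do so only if it were shown in the clinical report, and on that the protocol is silent.

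**Conclusion.** The conflict between 9.1.2 and sections 1.1 and 5 is real, and the masking of the surgeon is not assured as written. The conclusion rests on the literal wording of these sections, on the absence of a precedence statement, and on both documents being placed in one medical record with no stated access limit.

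The consequence for the primary outcome is conditional. It requires that the surgeon sees the site read and that this changes the extent or target of excision. The documents establish neither step. No size or direction of bias can be derived from them, and a claim that the primary result will be biased would go too far. What can be said is that the ambiguity applies to all 30 planned participants. It also could not be resolved afterwards, because no section provides for recording what the surgeon knew.

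This is a point that should be fixed, and not one on which the study's validity is shown to fail.

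**What to change.** Reconcile 1.1, 5 and 9.1.2 to one rule that states where the biopsy-site read is recorded and who may see it before excision. If the sponsor keeps its masking aim:

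1. Limit the 9.1.2 sentence on the clinical report to findings other than the biopsy site.
2. Hold the site read in the case report form, which already records it, or in a note with restricted access, and state the restriction.
3. State whether the overall BI-RADS code defined in 11.1 appears in the clinical report. If it does, explain how this fits the masking aim, since the code can reveal the site code.
4. Add one case report form item, referenced in 9.2.1, on what CESM information the surgeon had when the final plan was made.

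The cost is wording in 1.1, 5 and 9.1.2, a sentence in 11.1, a sentence in 9.2.1 and one data item. No extra reads or visits are needed. The downside is that the site read may reach the chart later than it otherwise would. The investigators must confirm that this is acceptable, and they decide when it is released.

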11.1 Study Design/Endpoints

The primary outcome will be whether the biopsy site on CESM is coded as benign or malignant and how that correlates with the pathologic diagnosis of the surgically excised specimen, as benign or malignant.

The biopsy site and up to 2 additional findings will be coded according to the Breast Imaging-Reporting and Data System (BI-RADS), ranging from 1-5. An overall code for each exam will then be generated that corresponds to the most suspicious finding in the study. BI-RADS codes 1, 2, and 3 associated with the corresponding categories of negative, benign findings, and probably benign findings will be classified as negative (benign). BI-RADS codes 4 and 5 associated with the corresponding categories of suspicious and highly suspicious for malignancy will be classified as positive (malignant).

Negative truth is defined by a benign diagnosis by the final outcome of pathologic review. Positive truth is defined by a malignant diagnosis (ductal carcinoma in situ and invasive cancer) by the final outcome of pathologic review.

The secondary outcome will be to understand the impact of CESM for ADH evaluation on surgical management. The pre-CESM and post-CESM final surgical management plans will be compared descriptively.

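### Section 9.1.2 sends the CESM consensus, biopsy site included, to the clinical report, while sections 1.1 and 5 keep the site out of it; if the site stays out, the secondary comparison cannot show the impact of the site read

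*Combined protocol and SAP*

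**What the plan says.** Section 9.1.2 defines the scope of the CESM read: "The CESM will be evaluated for the biopsy site and up to two additional findings in either breast". It describes what to look for at the biopsy site and then states: "The result of the consensus will be documented in the clinical" report (the last word follows a page break). It makes no exception for the site.

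Section 1.1 gives a different instruction: "The description of the site of atypia will be excluded from the clinical report and will be entered into a research note". Section 5 repeats that exclusion directly after saying "A clinical report will be generated and entered into the online medical record", and gives the reason: "This will ensure that the surgeon will not be biased by the CESM interpretation of the area of atypia".

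Two parts of section 11.1 depend on which instruction is followed. The primary outcome is the benign or malignant coding of the biopsy site on CESM and "how that correlates with the pathologic diagnosis of the surgically excised specimen, as benign or malignant". The secondary outcome reads: "The secondary outcome will be to understand the impact of CESM for ADH evaluation on surgical management"; it is assessed by a descriptive comparison of the plans before and after CESM. Section 11.2 calls it exploratory and words it as the impact on surgical management of ADH. Section 11.1 also says of the overall BI-RADS code: "An overall code for each exam will then be generated that corresponds to the most suspicious finding in the study".

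**The concern.** The plan sets up a safeguard in two places and contradicts it in a third. Withholding the site read keeps the surgery independent of the test being evaluated. A reader or coordinator working from 9.1.2, the section on how CESM is evaluated, would put the site read in front of the surgeon before excision. The primary outcome compares that read with what the surgeon removes.

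The safeguard also has a consequence that the plan does not state. A result that the surgeon never sees cannot change the surgeon's plan. Sections 11.1 and 11.2 nevertheless word the secondary outcome as the impact of CESM on the evaluation and management of ADH, which a reader could take to include the site read.

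**Working it through.** No arithmetic decides this point, so the check sets the sections side by side.

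**Step 1: is there a conflict?**

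| Section | What is read | Where the site read goes |
|---|---|---|
| 9.1.2 | Biopsy site and up to two other findings | Clinical report, as part of the consensus |
| 1.1 | Biopsy site and up to two other findings | Research note; excluded from the clinical report |
| 5 | (refers to 1.1) | Research note; excluded from the clinical report |

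The consensus in 9.1.2 includes the site, because that section names the site as part of the evaluation. All three sections are current text, and none says which prevails. The conflict is real.

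**Step 2: what follows if 9.1.2 is applied?** The clinical report goes into the online medical record (section 5). The surgeon could then know the site read before operating. The excised specimen is the reference standard (11.1), so the surgeon would be unmasked to the index test before the reference standard is obtained. That is the situation sections 1.1 and 5 set out to prevent.

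**Step 3: what follows if 1.1 and 5 are applied?** Any difference between the two plans can come from three sources: the CESM read of the site, other CESM findings, or something unrelated to CESM. Withholding the site read removes the first source by design. The other two remain. The comparison therefore cannot show the management impact of the site read, whether that impact would be large or nil.

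**Step 4: does withholding the description suffice?** Section 1.1 asks for a BI-RADS code for the overall exam, and 11.1 sets it to the most suspicious finding. Suppose the site is coded 4 and no other finding is above 2. The overall code is then 4. A clinical report that showed an overall 4 but described nothing above 2 would point to the site. The documents do not say whether the overall code appears in the clinical report, so this needs to be settled together with the description.

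**Step 5: do any figures change?** The 6 malignant and 24 benign patients in 11.2 rest on the significance level, power, sensitivity, specificity and incidence. None of these depends on where the site read is reported. Section 1.1 also has all individual and final interpretations recorded on case report forms, so the primary analysis has its data under either rule.

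**The case against.** The strongest reply is that the specific rule governs the general one. Sections 1.1 and 5 state the exclusion twice with its purpose, and 5 refers to 1.1 for the detailed design; 9.1.2 is one general sentence in a measurement section. Most readers would probably apply the exclusion, and nothing shows that staff would do otherwise. This stands as a reason to regard the conflict as a short drafting correction. It does not remove the conflict, because 9.1.2 names the site and no order of precedence is given.

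On the secondary outcome, the phrase in 11.1 can be read as CESM performed in women being evaluated for ADH. That fits objective 1.3, which concerns patients diagnosed with ADH, and section 9.2.1, which counts biopsies, surgical procedures and visits initiated by the exam. This also stands in part: no section promises an estimate for the site read alone, so one limiting sentence is enough and objective 1.3 needs no change.

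A reader might infer four stronger claims that the documents do not support:

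- *The primary result would be distorted by a definable amount.* Every participant is to have the ADH excised whatever CESM shows, and two pathologists with a tie-breaker review each specimen. The documents give neither a mechanism by which the read would change the pathological result nor a probability of it, so any figure would be invented.
- *The secondary outcome is empty.* It is not; other CESM findings can still change management, and 9.2.1 captures the procedures that they initiate.
- *An unchanged plan will be reported as no impact on ADH management.* No section specifies that conclusion, and the outcome is descriptive.
- *Masking already fails because the research note is in the online medical record.* The documents do not say whether the surgeon can open the note before excision. Silence on access is not a breach.

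**Conclusion.** The contradiction between 9.1.2 and sections 1.1 and 5 is established by the text alone and should be corrected. Followed literally, 9.1.2 would undo a stated safeguard for the primary comparison. How likely that is, and how far it would move the result, cannot be derived from the documents.

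The second part is conditional: if the site read is withheld, the plan comparison in 11.1 and 11.2 cannot show its impact on management. This assumes only that withholding works as sections 1.1 and 5 intend. It limits an exploratory outcome and does not invalidate it. No sample size, power or expected count changes.

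**What to change.** 1. Reconcile 9.1.2 with 1.1 and 5 so that all three say the same about where the biopsy-site read is reported. In the same edit, make any overall BI-RADS code shown in the clinical report follow that rule.
2. If the site read is withheld, add to 11.1: *Because the site read is withheld from the surgeon, this comparison reflects CESM findings other than the biopsy-site read and does not estimate the management impact of the site read.* If the sections are instead reconciled so that the site read is reported, state in 11.1 that the surgeon was not masked to it.

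The cost is a few lines in 9.1.2 and 11.1, with no added visit, test or participant. The downside is that, with the read withheld, the exploratory secondary outcome is explicitly narrower.
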